9.2. SECONDARY EFFICACY ENDPOINTS AND ANALYSES

9.2.1. Recovery with current FVIII (Screening Visit) versus 1st dose with Optivate® (Visit 1)

All recoveries will be calculated from incremental FVIII values (i.e. actual values minus pre-infusion values) using the vial label content as provided by BPL. FVIII values of less than 0.01 IU/mL will be regarded as zero. Incremental recovery will be determined from the peak value reached within 70 minutes post-infusion, samples taken after this time point will be discussed with the Sponsor and a decision whether to exclude the result will be made. Calculations will be based on the peak values obtained at actual post-infusion times, rather than those scheduled in the protocol.

Sponsor: BPL

Protocol: 8VWF07

Version: 1.0

Statistical Analysis Plan

FVIII levels will be reported in IU/dL and will be converted to IU/dL for the listings and calculation of incremental recovery.

Recovery = $\frac{\text{FVIII increment (IU/dL)}}{\text{FVIII dose (IU/kg)}}$

Recovery with current FVIII and first dose with Optivate® will be summarised.

Results will be tested for the normality of distribution using the Shapiro-Wilk test and if there is no strong evidence against normality, an Analysis of Variance (ANOVA) will be performed for the above recovery comparison.

The ANOVA model will include factors for subject and FVIII product (current FVIII versus Optivate®). Adjusted means for each product will be presented, in addition to the estimate and 95% confidence interval for the difference between products. The p-value for the hypothesis of equal recovery between the products will also be presented.

The analysis will be performed on both the Per Protocol and the Safety populations.

9.2.2. Recovery at 1 ED (Visit 1), 10-15 EDs (Visit 2), 50-75 EDs (Visit 3) and 100 EDs (Visit 4)

For Visit 1 (1 ED), Visit 2 (10-15 ED), Visit 3 (50-75 ED) and Visit 4 (100 ED), recovery will be calculated using the formula in 9.2.1.

Recovery will be summarised by visit, batch and subject.

An ANOVA will be performed to compare recovery values at Visit 1, Visit 2, Visit 3 and Visit 4. The model will include factors for subject and visit. Adjusted means for each visit will be presented, in addition to the estimates and 95% confidence intervals for the differences between visits. The p-value for the hypothesis of equal recovery between visits will also be presented.

An ANOVA will be performed to compare recovery values for each batch. The model will include factors for subject, visit and batch. Adjusted means for each batch will be presented, in addition to the estimates and 95% confidence intervals for the differences between batches. The p-value for the hypothesis of equal recovery between batches will also be presented.

The primary analysis will be performed using the Per Protocol Population. A secondary analysis will be conducted on the Safety Population. The summary by subject will be for the Safety population only.

Sponsor: BPL

Protocol: 8VWF07

Version: 1.0

Statistical Analysis Plan

9.2.3. Optivate® Therapy to Treat Break Through Bleeds

The following will be summarised using both the Per Protocol Population and Safety Population:

- The number and percentage of subjects with break-through bleeds and the number of break-through bleeds in total.
- The number of break-through bleeds per subject.
- The number and percentage of subjects with minor, major and emergency bleeds and the number of minor, major and emergency bleeds in total. This summary will be repeated but using assessments assigned by the investigator where this disagrees with the subject assessment. Should a bleed change severity, the worst case severity will be used in the summaries.
- The duration of bleeds (minutes), calculated for each individual bleed as: the stop time (in minutes) minus the start time (in minutes) + 1.

 Note, this summary will be based on the total number of bleeds.
- The number and percentage of subjects with bleeds located in the joint, muscle, open and other locations.
- The number and percentage of bleeds located in the joint, muscle, open and other locations.
- The number and percentage of subjects with spontaneous bleeds, bleeds due to injury and bleeds due to other causes.
- The number and percentage of spontaneous bleeds, bleeds due to injury and bleeds due to other causes.
- The total number of bleeds per subject will be summarized on a per year and on a per month basis.

The investigator's and subject's assessments of effectiveness of Optivate® to treat bleeds will be summarised separately. The tables will summarise the number and percentage of subjects with responses in each category, the best response for each subject, and the number and percentage of bleeds in each category. Summaries will be based on both the Per Protocol Population and Safety Population.

Sponsor: BPL

Protocol: 8VWF07

Version: 1.0

Statistical Analysis Plan

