7.8 Study Diaries

After the screening assessments have been conducted all subjects will be given a study diary to use during the study. The study diary is to enable comprehensive record of health information consistently for all subjects. In addition, subjects will be provided with a study diary manual explaining how to record the data and how this data needs to be returned to the site for regular review (see the study diary manual for more details).

The study diaries are to be completed when the subject has an adverse event or takes Optivate[®] or other medication (except herbal and homeopathic remedies) at home or at a local clinic (*ie* not the Investigational site) and with bleed details.

The diaries will record the following information:

- Optivate usage (home or at a local clinic).
- Details of any other AEs which occurred during home therapy. AEs that occur at site will be recorded on the CRF by the site staff; these will not be entered into the study diary to avoid duplication.
- Details of concurrent medication (excluding vitamins and herbal and homeopathic remedies) including name (preferably the generic name), dose, start date and stop date.
- Details of bleeds:
 - Duration (bleed start and stop time)
 - Location (joint, muscle or open/other).
 - Severity (major, minor or emergency). A major bleed is defined as a bleed that unacceptably restricts the patient's day-to-day life and an emergency bleed requires

urgent medical attention. In the case of emergency bleeds the study centre will be contacted. Clinicians will also review this data regularly and amend if necessary after discussing it with the subject (see Section 7.6).

- New bleed or ongoing bleed
- Cause (spontaneous bleeding, injury or other).
- Subjects will assess Optivate[®] therapy for each bleed as:
 - Very Helpful
 - o Helpful
 - Helped a little
 - Did not help
- The Investigator will also be assess Optivate[®] therapy for each bleed as:
 - Excellent
 - o Good
 - Moderate
 - o Poor

The study diaries will also record the following details of each dose of Optivate[®] administered at home or at the local clinic:

- Date and time of dose.
- Batch number.
- Whether the dose was administered as a preventative dose, a routine prophylactic dose or to treat a bleed.

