10.6.2 Secondary Endpoints

The secondary efficacy endpoints are the parameters described in Section 8.1.2 and safety variables in Section 8.2.

Recoveries

Results will be tested for the normality of distribution using the Shapiro-Wilk test and if normality is confirmed, an ANOVA will be performed for the recovery comparison (See Section 8.1.2.1 and 8.1.2.2).

Descriptive statistics will be presented on the number of recoveries at each timepoint and for each subject. These will be presented for each visit and for each subject and then for each batch of FVIII/ Optivate[®] used (see Section 8.1.2.1 and 8.1.2.2). Overall descriptive statistics will also be present for all subjects and all batches.

Bleeds

Bleed data will be summarised using summary statistics on two different bases: with each bleed as the experimental unit, and also with each subject as the experimental unit. Severity, duration of bleed, location and cause of bleed will be summarised separately, as well as being summarised in total. The treatment of new bleeds and ongoing bleeds will be listed. Also see Section 8.1.2.3.

Clinician's and subject's judgement of break-through bleed of treatment outcome

The data for clinician's and subject's assessment of bleeds will tabulated on separate tables, including the count for the number of bleeds not assessed. The tables will display the number and percentage of bleeds assessed for each category (*eg* very helpful, helpful etc.). This will be presented: Using all bleeds as the denominator and also the number of bleeds assessed as the denominator, displaying the number of bleeds not assessed.

Optivate[®] consumption

Dosing data will be summarised by treatment type *ie* prophylactic, preventative, to treat a bleed and overall. Total consumption data will be summarised using summary statistics on a per infusion and a per subject basis. Overall consumption data will be listed for each subject and summary statistics will also be displayed per month and year on a per subject basis (also see Section 8.1.2.4). Where a subject has completed less than a year of Optivate[®] treatment, the data will be extrapolated to calculate the per year consumption.

Exposure days

An exposure day is defined as a day in which the subject has received at least one dose of Optivate[®] (irrespective of treatment). The number of EDs will be listed for each subject. Descriptive statistics will be presented on a per month, per year and overall basis (also see Section 8.1.2.4).

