5.2. SECONDARY EFFICACY ENDPOINTS

The secondary efficacy endpoints are:

- Recovery with current FVIII (screening Visit) versus 1st dose with Optivate[®] (Visit 1).
- Recovery at 1 ED (Visit 1), 10-15 EDs (Visit 2), 50-75 EDs (Visit 3) and 100 EDs (Visit 4).
- Number of break through bleeds including severity, duration, location and cause.
- Clinician's judgment of break-through bleed treatment outcome (excellent, good, moderate, poor).
- Subject's judgment of break-through bleed treatment outcome (very helpful, helpful, helped a little, did not help).
- Number of exposure days for each subject and per month/subject, per year/subject and overall.
- Total dose in IU/kg of Optivate® and average dose per infusion for prophylactic use, to treat a bleed, any additional preventative use and overall use; all analysed on a per subject basis.
- Total number of infusions for prophylactic use, to treat a bleed, any additional preventative use and overall use; all analysed on a per subject basis.
- Mean dose in IU/kg of Optivate® per subject/month and per subject/year for prophylactic use, to treat a bleed, any additional preventative use and overall use; all analysed on a per subject basis.

Sponsor: BPL

Protocol: 8VWF07

Version: 1.0

Statistical Analysis Plan

 Mean number of infusions per subject/month and per subject/year for prophylactic use, to treat a bleed, any additional preventative use and overall use; all analysed on a per subject basis.

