7. GENERAL ASPECTS FOR STATISTICAL ANALYSIS

7.1. GENERAL METHODS

Statistical outputs will be generated using SAS version 9.3 (or later).

The study only has one treatment and so all summary tables will have a single results column for Optivate[®]. However, if subjects suffering from severe haemophilia A with basal FVIII values of < 2% rather than < 1% are recruited into the study, an additional two results columns will be presented, one for subjects with a basal FVIII < 1%, and one for subjects with a basal FVIII $\ge 1\%$ (see Section 6.3).

Continuous variables will be summarised using the number of observations (n), mean, 95% confidence interval for the mean, standard deviation (SD), median, minimum, and maximum. Minima and maxima will be quoted to the number of decimal places as recorded in the CRF, means and medians will be quoted to one further decimal place, and SDs will be quoted to one further decimal place than the mean value. Categorical variables will be summarised using number of observations (n), frequency and percentages of subjects. Percentages will be rounded to one decimal place, with the exception of 0% and 100%, which will be presented to no decimal places.

All relevant subject data will be included in listings. All subjects entered into the database will be included in subject data listings.

Data from unscheduled visits will not be included in the summary tables. These data will be listed only.

Where multiple data/results are available at a given visit for the same parameter, the first non-missing result will be used in the summary tables. All data will however be listed.

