16. INDEX OF TABLES

- Table 14.1.1 Subject Disposition, All Screened Subjects
- Table 14.1.2 Study Duration, Safety Population
- Table 14.1.3 Demographics and Baseline Characteristics, Safety Population
- Table 14.1.4 Medical History, Safety Population
- Table 14.1.5.1 Prior Medications, Safety Population
- Table 14.1.5.2 Concomitant Medications, Safety Population
- Table 14.2.1.1 FVIII Inhibitor Status, Per Protocol Population
- Table 14.2.1.2 FVIII Inhibitor Status, Safety Population
- Table 14.2.1.3 Shifts in FVIII Inhibitor Status, Per Protocol Population
- Table 14.2.1.4 Shifts in FVIII Inhibitor Status, Safety Population
- Table 14.2.1.5 Number of Exposure Days Until the Development of Inhibitors (Positive Status), Per Protocol Population
- Table 14.2.1.6 Number of Exposure Days Until the Development of Inhibitors (Positive Status), Safety Population
- Table 14.2.2.1 Recovery of Current Factor VIII and First Dose of Optivate, Per Protocol Population
- Table 14.2.2.2 Recovery of Current Factor VIII and First Dose of Optivate, Safety Population
- Table 14.2.3.1 Optivate Recovery (IU/dL per IU/kg) by Visit, Per Protocol Population
- Table 14.2.3.2 Optivate Recovery (IU/dL per IU/kg) by Visit, Safety Population
- Table 14.2.3.3 Optivate Recovery (IU/dL per IU/kg) by Batch, Per Protocol Population
- Table 14.2.3.4 Optivate Recovery (IU/dL per IU/kg) by Batch, Safety Population
- Table 14.2.3.5 Optivate Recovery (IU/dL per IU/kg) by Subject, Safety Population
- Table 14.2.4.1 Bleeds by Subject, Per Protocol Population
- Table 14.2.4.2 Bleeds, Per Protocol Population
- Table 14.2.4.3 Bleeds by Subject, Safety Population
- Table 14.2.4.4 Bleeds, Safety Population
- Table 14.2.5.1 Investigator's Assessment of Effectiveness of Optivate, Per Protocol Population
- Table 14.2.5.2 Investigator's Assessment of Effectiveness of Optivate, Safety Population
- Table 14.2.6.1 Subject's Assessment of Effectiveness of Optivate ,Per Protocol Population
- Table 14.2.6.2 Subject's Assessment of Effectiveness of Optivate, Safety Population
- Table 14.2.7.1 Optivate Exposure Days, Per Protocol Population
- Table 14.2.7.2 Optivate Exposure Days, Safety Population
- Table 14.2.7.3 Total Optivate Dose, Per Protocol Population
- Table 14.2.7.4 Total Optivate Dose, Safety Population
- Table 14.2.7.5 Total Optivate Infusions, Per Protocol Population
- Table 14.2.7.6 Total Optivate Infusions, Safety Population
- Table 14.2.7.7 Optivate Dose per Infusion, Per Protocol Population

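### SAP 9.2.3 summarises bleed duration per bleed only, although Protocol 10.6.2 also requires it per subject; the interval that remains ignores repeat bleeds within subjects, and SAP 12 declares no change

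*SAP*

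**What the plan says.** Protocol 10.6.2, under Bleeds, requires summaries "on two different bases: with each bleed as the experimental unit, and also with each subject as the experimental unit". Its next sentence names the variables: "Severity, duration of bleed, location and cause of bleed will be summarised separately, as well as being summarised in total". Duration belongs to a listed secondary endpoint (SAP 5.2): "Number of break through bleeds including severity, duration, location and cause".

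SAP 9.2.3 carries both bases over for the categorical items. For location, for example, it plans "The number and percentage of subjects with bleeds located in the joint, muscle, open and other locations" and then the same breakdown counted by bleeds. For duration, it defines a value in minutes for each individual bleed and adds: "Note, this summary will be based on the total number of bleeds". It specifies no subject-level duration summary.

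SAP 7.1 sets the default statistics: "Continuous variables will be summarised using the number of observations (n), mean, 95% confidence interval for the mean", followed by SD, median, minimum and maximum. Protocol 10.3 sets the same default, including the interval, unless otherwise stated. SAP 12 says that nothing differs from the protocol's analyses.

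**The concern.** Two things follow from the duration note.

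- The SAP drops one of two summaries that the protocol asks for, and SAP 12 does not report it.
- The summary that is left pools all bleeds. Its interval counts several bleeds from one subject as separate, independent observations, and its mean gives each subject a weight proportional to his number of bleeds. With 10 to 12 subjects, a few frequent bleeders could shape the mean, and the interval could look narrower than so few subjects justify. The subject-basis summary is what would let a reader see this.

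**Working it through.** **Step 1: compare the texts.**

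| Bleed variable | Protocol 10.6.2 | SAP 9.2.3 |
|---|---|---|
| Severity | bleed and subject | bleed and subject |
| Location | bleed and subject | bleed and subject |
| Cause | bleed and subject | bleed and subject |
| Duration | bleed and subject | bleed only |

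The omission is established here and needs no assumption.

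**Step 2: inputs for the size of the effect.** The documents give 10 evaluable subjects from 12 enrolled, and no bleed counts, intraclass correlation (ICC) or duration distribution. There is no planned figure to reproduce, because no formal sample size was calculated. Assumptions: m = 2, 5 or 10 bleeds per subject; ICC 0.1, 0.3 or 0.5; normal durations with a random subject effect and total variance 1.

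**Step 3: design effect.** DEFF = 1 + (m − 1) × ICC, and the true standard error is √DEFF times the one that assumes independence.

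- m = 2, ICC 0.1: DEFF = 1 + 1 × 0.1 = 1.1.
- m = 5, ICC 0.3: DEFF = 1 + 4 × 0.3 = 2.2. The 50 bleeds carry the information of 50 / 2.2 = 22.7, and the standard error is understated by a factor of √2.2 = 1.48.
- m = 10, ICC 0.5: DEFF = 1 + 9 × 0.5 = 5.5. The 100 bleeds are worth 100 / 5.5 = 18.2.

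**Step 4: coverage of the nominal 95% interval**, by simulation with 20,000 replicates and 10 subjects. The pooled interval is mean ± t(10m − 1) × SD / √(10m). The subject interval is mean of subject means ± t(9) × SD of subject means / √10.

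| Bleeds each | Pooled, ICC 0.1 | Pooled, ICC 0.3 | Pooled, ICC 0.5 | Subject means |
|---|---|---|---|---|
| 2 | 94% | 91% | 89% | about 95% |
| 5 | 90% | 81% | 73% | about 95% |
| 10 | 85% | 69% | 59% | about 95% |

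At ICC 0 the pooled interval covers about 95% for every m. With one bleed each the two intervals are identical. Results for 12 subjects agree within about one point. At m = 5 and ICC 0.3, the pooled interval averages 0.56 SD wide and the subject-mean interval 0.92 SD, a ratio of 0.92 / 0.56 = 1.64.

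**Step 5: unequal bleeding.** Take 30 bleeds, 12 in one subject and 2 in each of nine. The frequent bleeder has weight 12 / 30 = 40% in the pooled mean, against 1 / 10 = 10% on a subject basis. Pooled coverage is about 89% / 79% / 69% at ICC 0.1 / 0.3 / 0.5.

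**Step 6: skewed durations.** With lognormal durations (log-SD 1, ICC 0.3 on the log scale, 10 subjects):

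| Bleeds each | Pooled | Subject means |
|---|---|---|
| 1 | 84% | 84% |
| 2 | about 84% | 87% |
| 5 | about 80% | 89% |
| 10 | 72% | 91% |

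Neither interval reaches 95%. The subject-mean interval is closer to it whenever subjects have repeat bleeds.

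**The case against.** **The SAP did not create the pooled interval.** This stands. Protocol 10.3 has the same default, and Protocol 10.6.2 itself asks for a per-bleed summary, so a SAP that followed the protocol fully would still print a pooled interval. SAP 9.2.3 does not name an interval for duration either; it comes from the general rule. What the SAP removed is the subject-basis summary beside it.

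**The size is assumed.** This also stands. With few bleeds per subject or little correlation the loss is small, and under skewness subject means do not restore 95%. The omission itself does not depend on these assumptions.

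**The table shells may contain the missing row.** The index lists "Table 14.2.4.1 Bleeds by Subject, Per Protocol Population" and a matching Safety Population table, and the mock-ups are a separate attachment that is not available here. One can argue that the duration note governs only the summary it is attached to and forbids no other. Even so, the only duration summary that the SAP text specifies is per bleed, and a table title does not supply the other.

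**It is descriptive and recoverable.** This is true as well. The median and range are also planned, bleeds per subject are summarised, and the bleed listing would allow per-subject durations to be rebuilt. But the method would then be chosen after the data are seen.

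**Conclusion.** The point holds as an undeclared departure of the SAP from the protocol: the subject-basis summary of bleed duration is missing. The remaining per-bleed interval is unreliable to the extent that durations correlate within subjects. Under normal durations and the assumed ranges, its coverage with 10 subjects is about 94% to 59%, with no loss from clustering at ICC 0 or one bleed each.

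A reader might infer more than the documents support:

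- That the SAP introduced the flawed interval. Protocol 10.3 already implies it.
- That under-coverage of a given size will occur. Neither bleed counts nor correlation is documented.
- That efficacy conclusions or the inhibitor result are at risk. No hypothesis test is planned on duration, and the primary endpoint does not use it.
- That a subject-mean interval guarantees 95%. It does so only under roughly normal durations.

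The consequence is limited to descriptive tables for part of a secondary endpoint, but the correction is cheap and worth making before the analysis.

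**What to change.** 1. In SAP 9.2.3, add the subject-basis duration summary: one mean or median duration per subject with at least one bleed, summarised across subjects in Tables 14.2.4.1 and 14.2.4.3. State how many subjects contribute, since those without bleeds drop out and the number may be below 10.
2. Keep the per-bleed summary, but omit its 95% confidence interval or compute it with subject as the cluster.
3. Record item 2 in SAP 12 as a change from the Protocol 10.3 default. If the subject basis is left out on purpose, record that in SAP 12 instead, with the reason.

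The cost is a few lines of SAP text and one block in tables already planned. No new data are needed, because the diary already records bleed start and stop times (Protocol 7.8).

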10.2. ADVERSE EVENTS

Adverse events will be coded to system organ classes and preferred terms using MedDRA version 16.1.

Treatment emergent AEs are defined as events that have onset following the first infusions of Optivate®, or events present before the first infusion of Optivate®, but which worsen in severity following the first infusion of Optivate®. Should the time of onset be missing, but the date of onset be equal to the date of first dosing with Optivate®, then it will be assumed such events are treatment emergent.

Should the day of onset be missing, for the purposes of assigning treatment emergence, the day will be taken to be 01, unless the month and year are the same as the month and year of first infusion of Optivate[®], in which case the date of first infusion of Optivate[®] will be taken.

Should the day and month be missing, for the purposes of assigning treatment emergence, the day and month will be taken to be 01 January, unless the year is the same as the year of first infusion of Optivate®, in which case the date of first infusion of Optivate® will be taken.

All adverse events will be listed, however only treatment emergent adverse events will be included in the summary tables.

Sponsor: BPL

Protocol: 8VWF07

Version: 1.0

Statistical Analysis Plan

Where severity or causality is missing for an event, for the purposes of the tables, these will be assumed to be severe and very likely/certain respectively. Similarly, where severity or causality changes during the course of the event, the worst case will be taken for the analysis.

Summary tables presenting frequency of AEs by SOC and PT will be ordered by overall descending frequency of SOC and then, within a SOC, by overall descending frequency of PT.

The following tables of adverse events will be produced:

- An overall summary of the number and percentage of subjects reporting TEAEs, serious TEAEs, treatment related TEAEs, TEAEs leading to withdrawal and TEAEs leading to death
- TEAEs overall and by system organ class and preferred term
- Study treatment related TEAEs overall and by system organ class and preferred term. Study-treatment related events are those recorded as having a possible, probable, or very likely/certain causality related to Optivate®.
- TEAEs by maximum severity, overall and by system organ class and preferred term
- Serious TEAEs, overall and by system organ class and preferred term

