14.2.5.2. Table Conventions

- Units will be included where available
- If the categories of a parameter are ordered, then all categories between the maximum and minimum category should be presented in the table, even if n=0 for all treatment groups in a given category that is between the minimum and maximum level for that parameter. For example, the frequency distribution for symptom severity would appear as:

Severity	N
Rating	
severe	0
moderate	8
mild	3

Where percentages are presented in these tables, zero percentages will not be presented and so any counts of 0 will be presented as 0 and not as 0 (0%).

- Unless otherwise specified in the mock table, where the categories are not ordered (e.g., Medical History, Reasons for Discontinuation from the Study, etc.), then only those categories for which there is at least 1 subject represented in 1 or more groups should be included.
- Unless otherwise specified, the estimated mean and median for a set of values should be printed out to 1 more significant digit than the original values, and standard deviations should be printed out to 2 more significant digits than the

Sponsor: BPL
Protocol: 8VWF07

Version: 1.0

Statistical Analysis Plan

original values. The minimum and maximum should report the same significant digits as the original values. For example, for systolic blood pressure:

N	XX
Mean	XXX.X
Std Dev	X.XX
Median	XXX.X
Minimum	XXX
Maximum	XXX

- P-values should be output in the format: "0.xxx", where xxx is the value rounded to 3 decimal places. Any p-value less than 0.001 will be presented as <0.001. If the p-value should be less than 0.0001 then present as <0.0001. If the p-value is returned as >0.999 then present as >0.999
- Percentage values should be printed to one decimal place, in parentheses with no spaces, one space after the count (e.g., 7 (12.8%), 13 (5.4%)). Unless otherwise noted, for all percentages, the number of subjects in the analysis population for the treatment group who have an observation will be the denominator. Percentages after zero counts should not be displayed and percentages equating to 100% should be presented as 100%, without any decimal places.

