- The percentage of subjects is normally calculated as a proportion of the number of subjects assessed in the relevant treatment group (or overall) for the analysis population presented. However, careful consideration is required in many instances due to the complicated nature of selecting the denominator, usually the appropriate number of subjects exposed.
- For categorical summaries (number and percentage of subjects) where a subject can be included in more than one category, describe in a footnote or programming note if the subject should be included in the summary statistics for all relevant categories or just 1 category and the criteria for selecting the criteria.
- Where a category with a subheading (such as system organ class) has to be split over more than one page, output the subheading followed by "(cont)" at the top of each subsequent page. The overall summary statistics for the subheading should only be output on the first relevant page.

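### Does the per-subject best response in SAP 9.2.3, with the protocol's bleed denominators left unstated, distort the bleed-treatment ratings?

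*SAP*

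**What the plan says.** Protocol 10.6.2 (Secondary Endpoints) sets out separate clinician and subject rating tables with the bleed as the unit: "The tables will display the number and percentage of bleeds assessed for each category". Percentages are to be given on two bases: "Using all bleeds as the denominator and also the number of bleeds assessed as the denominator, displaying the number of bleeds not assessed". For bleed data in general, the same section asks for summaries "with each bleed as the experimental unit, and also with each subject as the experimental unit". Protocol 8.1.2.3 lists only the two judgements and their four categories each. Neither section mentions a best response.

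SAP 9.2.3 plans three things for each rater: subjects by category, then "the best response for each subject, and the number and percentage of bleeds in each category". It names no bleed denominator and no count of unrated bleeds. It also does not say how a subject with mixed ratings enters the subject rows. The general convention in SAP 14.2.5.2 is worded for subjects ("the number of subjects in the analysis population for the treatment group who have an observation will be the denominator"). That section leaves to a footnote or programming note the choice of "if the subject should be included in the summary statistics for all relevant categories or just 1 category". SAP 12 declares no change from the protocol. The table mock-ups are a separate attachment (SAP 19.1) and are not in the public documents.

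**The concern.** Three things look wrong on a first reading.

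- Best response is the maximum over a subject's bleeds, so a subject who bleeds more has more chances of a good rating. It can show excellent for someone with a poor outcome on another bleed. It also seems to run against the SAP's habit elsewhere. For bleed severity, "Should a bleed change severity, the worst case severity will be used in the summaries"; for adverse events, "where severity or causality changes during the course of the event, the worst case will be taken for the analysis".
- The subject-by-category rows would balance it only if a subject counts in every category received, and SAP 9.2.3 does not state that rule.
- If the subject-based default is applied to bleeds by analogy, unrated bleeds drop out of the denominator and the percentages can look better than the protocol intended.

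At stake is how favourable the bleed-treatment tables look to a reader. No test is planned on them.

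**Working it through.** **1. Is there a figure to reproduce?** No. The documents give no bleed counts, rating rates or unrated fraction. Every rate below is an assumption, used only to show direction and range.

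**2. Best response read alone.** Let *q* be the chance that a bleed is rated excellent, *k* the bleeds per subject and *r* the within-subject correlation.

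- Independent ratings: P(best = excellent) = 1 − (1 − q)^k. With q = 0.40 and k = 3: 1 − 0.6³ = 1 − 0.216 = 0.784.
- Correlated ratings (beta-binomial): 1 − B(a, b + k)/B(a, b), with a = q(1 − r)/r and b = (1 − q)(1 − r)/r. With r = 0.5, a = 0.4 and b = 0.6, so at k = 3: 1 − (0.6 × 1.6 × 2.6)/(1 × 2 × 3) = 1 − 0.416 = 0.584.

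| r | 1 bleed | 3 bleeds | 5 bleeds |
|---|---|---|---|
| 0 | 40.0% | 78.4% | 92.2% |
| 0.3 | 40.0% | 66.1% | 76.2% |
| 0.5 | 40.0% | 58.4% | 65.6% |
| 1 | 40.0% | 40.0% | 40.0% |

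Now assume also that 10% of bleeds are rated poor. With three independent bleeds, P(any poor) = 1 − 0.9³ = 0.271. P(any excellent and any poor) = 1 − 0.216 − 0.729 + 0.125 = 0.180. So 0.180/0.271 = 66% of subjects with a poor bleed still show excellent as best response. At r = 0.3, 0.5 and 1 the figure is 51%, 40% and 0%. The property is real, and the range includes no effect.

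**3. Best response read with the rows beside it.** Take an extreme assumed case: 10 subjects with 5 bleeds each, 1 rated excellent and 4 poor.

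- Best response: 10/10 = 100% excellent.
- Bleed rows: 10/50 = 20% excellent, 40/50 = 80% poor.
- Subject rows, counting every category received: 100% excellent and 100% poor.
- Subject rows, counting once at best: 100% excellent and 0% poor.

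Whichever counting rule is used, the bleed rows in the same table show 80% poor. The best-response row cannot hide it.

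**4. Which counting rule is meant?** The SAP lists subjects by category and best response as separate outputs. Counting each subject once, at best, would make the first a copy of the second. Counting a subject in every category received is the reading that gives both a purpose. It also fits the neighbouring items in SAP 9.2.3, which count subjects with each bleed severity, location and cause. SAP 14.2.5.2 places this rule in a footnote or programming note, so its absence from the prose follows the SAP's own layout.

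**5. The two denominators.** Assume 50 bleeds, 30 of them rated good or better.

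| Unrated | Of assessed bleeds | Of all bleeds |
|---|---|---|
| 0 | 30/50 = 60.0% | 60.0% |
| 5 | 30/45 = 66.7% | 60.0% |
| 10 | 30/40 = 75.0% | 60.0% |
| 15 | 30/35 = 85.7% | 60.0% |

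The gap matters if many bleeds are unrated, but the information is not lost. Provided each rater gives one rating per bleed (Protocol 7.8), the category counts sum to the number assessed. SAP 9.2.3 also plans the total number of bleeds. Unrated = total − sum of category counts, and the all-bleeds percentage = category count/total. With 10 unrated, 50 − 40 = 10 and 30/50 = 60.0%. The bleed tables (14.2.4.1 to 14.2.4.4) and the rating tables (14.2.5.1–2 and 14.2.6.1–2) are planned for the same two populations, so totals and counts match.

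**6. The worst-case comparison.** The severity and adverse-event rules resolve several values within one bleed or one event. Best response selects across a subject's separate bleeds, so these are different operations and the contrast shows no inconsistency.

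**The case for a change.** The strongest opposing case is that Protocol 10.6.2 is explicit on both denominators and the unrated count, SAP 9.2.3 repeats neither, and SAP 12 says nothing has changed. The two raters assess separately, so unrated bleeds could differ between the two tables. Best response is also a one-directional addition with no worst response beside it. Some SAP rules do select the worse value across several assessments of one subject: inhibitor status over unscheduled visits (SAP 9.1), and maximum adverse-event severity per subject (SAP 10.2).

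Part of this stands. SAP 9.2.3 is less complete than the protocol on denominators, and best response is an SAP addition. The rest carries less weight. The SAP's silence does not withdraw a protocol requirement, and an analyst building these tables works from both documents. The mock-ups, where such rows would normally appear, are not available, so an omission from the tables themselves cannot be shown. The protocol calls for bleed data by subject as well as by bleed, so a subject-level summary is within its scope; which statistic to use is a matter of presentation. An extra descriptive row replaces no planned analysis, so it does not contradict SAP 12. The inhibitor and adverse-event rules are safety conventions, and they do not oblige an efficacy rating to be shown at its worst.

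**Conclusion.** No change to the plan is needed. Best response does rise with the number of bleeds: from 40% to between 40% and 78% of subjects at three bleeds each, under the assumed 40% excellent rate and correlations from 1 down to 0. It is correctly labelled, however, and is planned in the same sentence as the bleed-level and subject-level distributions that show the full picture. The counting rule is evident from listing the two subject outputs separately. The unrepeated denominators are a clerical gap: the protocol still requires them, and both percentages and the unrated count follow from numbers already planned.

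This conclusion rests on two conditions: that analysts apply Protocol 10.6.2 together with SAP 9.2.3, and that category counts are shown alongside percentages, as the SAP plans. The summary is descriptive and secondary, in about 10 subjects. No test, sample-size figure or primary inhibitor result depends on it.
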